4.6 End of Study Definition

The end of study is defined as the date of the last visit of the last subject in the study. A subject is considered to have completed the study if they have completed all periods of the study from Screening up to and including the EoS visit for those subjects not who will not participate in the OLE. Subjects who withdraw prematurely from the study will attend an EoS visit and will not be eligible to progress to the OLE study.

At the time of study completion or EoS visit, subjects will be queried regarding any AEs, concomitant medications, and concurrent procedures, which will be recorded on the appropriate page(s) of the source documents and electronic case report form (eCRF). At the final study visit, subjects with ongoing AEs that are considered by the Investigator to be serious, study drug-related, or associated with the target condition will be requested to continue to follow up with the Investigator until the AE resolves, is stable, or follow-up is no longer possible/necessary. Any death or pregnancy that occurs while on study (or, for subjects not participating in the OLE study, within 28 days after the subject's last dose of study drug) must be reported to the Sponsor/designee for the study within 24 hours after the center becomes aware of the event.

4.7 Criteria for Study/Site Termination

Both the Sponsor and the Investigator reserve the right to terminate the study according to the study contract. The Sponsor may issue a protocol amendment or discontinue the study entirely, based on regulatory authority or Institutional Review Board/Independent Ethics Committee (IRB/IEC) recommendations, drug safety or availability concerns, discontinuation of the development program for lorundrostat, or at the Sponsor's discretion, with at least 30 days' notice. The DMC may also recommend study termination based on a review of the safety data.

4.8 Study Conduct

A schedule of study assessments is presented in the Schedule of Assessments (**Table 1**). Details of study assessments are provided in the Study Reference Manual (SRM) and [Section 8](#) of this protocol.

4.9 Modifications to Study Conduct Due to Global Pandemics

In an aftermath of the COVID-19 pandemic that has had a worldwide impact, some modifications to study conduct during a global epidemic/pandemic including, but not limited to, COVID-19 may be necessary to ensure study continuity, including conducting virtual visits when on-site study visits are considered not feasible. Such modifications in study conduct must always be in accordance with local regulations/mandates.

The following are allowable, as necessary, modifications to study conduct during a global epidemic/pandemic:

- Prior to a study visit at the site, the subject may be contacted and screened for potential exposure or infection to any pathogen associated with a global epidemic/pandemic, including but not limited to COVID-19, per site, local, or federal requirements. If the subject is suspected to be exposed to or infected with such a pathogen, the on-site visit should either be rescheduled or a virtual visit may be performed instead, if feasible.
- If a subject cannot attend their regularly scheduled study visits in person due to an exposure to or an infection with any pathogen associated with a global epidemic/pandemic, the Investigator may consider performing safety and efficacy assessments by phone or video, if feasible. Virtual assessments may include home BP evaluation, AEs, and concomitant medication review. Virtual assessments should be recorded by site staff in the source documents.
- Clinical laboratory and pregnancy tests may be performed by local laboratory, if sample collection cannot be performed at the study site due to limitations associated with a global epidemic/pandemic (e.g., site closure). Abnormal laboratory results should be promptly communicated to the Medical Monitor. Subjects' confidentiality must be maintained when communicating results to the Medical Monitor.
- At home study drug administration may continue for up to 2 weeks (at multiple times during the study if required due to a global epidemic/pandemic, although not consecutively) if the subject has no relevant clinically significant out of range values per previous laboratory reports.
- Source documentation should note that the visit was performed virtually and note the name of the local laboratory where laboratory tests were done, if applicable.
- If certain study procedures or assessments (e.g., laboratory tests, vital signs, physical examinations) cannot be completed per the Schedule of Assessments due to a global

epidemic/pandemic, the reason for the missed assessment must be noted in the source documentation, captured in the protocol deviations documentation, and reported to the IRB/IEC if applicable.

A detailed assessment of risks and risk mitigation measures related to any pathogen associated with a global epidemic/pandemic including, but not limited to, COVID-19, should be documented in the appropriate study documents, as applicable.

5. STUDY POPULATION

Subjects not meeting all inclusion criteria, or meeting at least one exclusion criterion, may be re-screened if there is a reasonable probability of reversal. Retesting of laboratory samples, and a repeat AOBP assessment is allowed in the event of technical failure. Inclusion in the study of any subject who meets all eligibility criteria on rescreening will be at the discretion of the Investigator.

5.1 Inclusion Criteria

Subjects eligible for inclusion in this study must meet **all** the following criteria:

1. Written informed consent, obtained before any study-related assessment is performed
2. At least 18 years of age at the time of signing the informed consent form (ICF)
3. At Screening, UACR of 200-5000 mg/g, inclusive, in first morning urine void
4. At Screening, eGFR of ≥ 30 mL/min/1.73 m²
5. At Screening, AOBP SBP of 135-180 mmHg, inclusive
6. At Randomization, AOBP SBP of 135-180 mmHg, inclusive
7. On a stable treatment with an ACEi or ARB for at least 4 weeks prior to Screening
8. At Screening, serum cortisol (morning measurement, blood draw as close to 8 AM as possible between 3 and 22 µg/dL, inclusive)
9. At Screening, body mass index (BMI) of ≥ 18 kg/m²
10. Fertile male subjects and female subjects of childbearing potential must agree to use an acceptable method of contraception ([Appendix 12.4](#)) from the Screening Visit to 28 days after the last dose of study drug in each study part
11. Willing and able to comply with the study instructions and attend all scheduled study visits, and are capable of providing informed consent

5.2 Exclusion Criteria

Subjects meeting any of the following criteria are **not** eligible for inclusion in this study:

1. Women who are pregnant, plan to become pregnant, or are breast-feeding
2. Subjects with known hypersensitivity to lorundrostat or any of its respective excipients
3. Subjects with known hypersensitivity to dapagliflozin or any of its respective excipients (subjects beginning dapagliflozin only)
4. Treatment, or anticipated treatment, with any prohibited medication within the timeframes described in [Section 6.9](#) of this protocol.
5. Treatment, or anticipated treatment, with triamterene and amiloride
6. Participation in a trial involving an investigational device or drug within 4 weeks or 5 half-lives (whichever is longer) prior to the Screening Visit
7. Previous treatment with lorundrostat or other ASI within 4 weeks or 5 half-lives (whichever is longer) prior to the Screening Visit

8. At Screening, serum potassium >5.0 mmol/L
9. At Randomization, serum potassium >5.0 mmol/L (prior to first dosing of study drug)
10. At Screening, serum sodium <135 mmol/L (corrected for hyperglycemia using the Katz formula). Rescreening of subjects with an exclusionary serum sodium is only allowed if two consecutive measurements at least one week apart are ≥ 135 mmol/L
11. Total bilirubin $>2\times$ upper limit of normal (ULN) except for those with a diagnosis of Gilbert's syndrome, unless approved by Medical Monitor
12. History of clinically significant hyponatremia within 1 year prior to Screening
13. History of adrenal insufficiency or an abnormal ACTH stimulation test within 1 year prior to Screening
14. Hospitalization for the treatment of urgent or emergent hypertension within 1 year prior to Screening
15. Current, known or presumed white coat hypertension/significant white coat effect (as defined in the SRM)
16. Current, known or presumed orthostatic hypotension
17. Current, known or presumed autonomic dysfunction
18. Arm circumference >55 centimeters at Screening
19. Subjects with a previously proven secondary cause of hypertension are excluded with the following exceptions:
 - a. Subjects with documented sleep apnea are eligible to participate
 - b. Subjects with documented primary hyperaldosteronism are eligible to participate if they discontinue use of a MRA. They should have <20 mmHg increase in AOBP SBP, and AOBP SBP <150 mmHg at Randomization. MRA treatment may be tapered over a one-week period.
20. Use of epithelial sodium channel (ENaC) inhibitors or MRAs, including, but not limited to amiloride, triamterene, spironolactone, eplerenone, finerenone, from 4 weeks prior to the Screening Visit and during study participation. With the exception of MRAs in primary aldosteronism.
21. Medical history of kidney disease related to autoimmune diseases (lupus, anti-neutrophil cytoplasmic antibody [ANCA] vasculitis), multiple myeloma or other known paraproteins, infiltrative diseases of the kidney, obstructive nephropathy, cystic kidney diseases, and renal transplantation
22. Medical history of advanced liver disease, including cirrhosis
23. Medical history of active autoimmune disease or recent (within 30 days) or anticipated need for immunosuppressive therapy
24. Subjects with a medical history of urosepsis and pyelonephritis, lower limb amputation, genital mycotic infections, necrotizing fasciitis of the perineum (Fournier's Gangrene)
25. History of heart failure, myocardial infarction, stroke, or transient ischemic attack within 6 months prior to Screening. Heart failure of New York Heart Association (NYHA) Class II or more requires approval by the Medical Monitor

26. Diabetes mellitus with a glycosylated hemoglobin (HbA_{1c}) >10% (>86 mmol/mol) at Screening
27. Planned major surgery requiring hospitalization during the study period or performed within 4 weeks prior to the Screening Visit
28. History of malignant neoplasms within the 5 years prior to Screening except for known history of basal and squamous cell skin cancer and any carcinoma *in-situ*
29. Known or suspected abuse of illicit drugs or alcohol within 1 year prior to the Screening Visit
30. In the opinion of the PI, any other condition that will preclude participation in the study

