27. Diabetes mellitus with >1 severe hypoglycemic event or severe diabetic ketoacidosis event (events requiring external help) in the 12 months prior to Screening, or with a history of impaired hypoglycemia awareness at Screening
28. Planned major surgery requiring hospitalization during the study period or performed within 4 weeks prior to the Screening Visit
29. History of malignant neoplasms within the 5 years prior to Screening except for known history of basal and squamous cell skin cancer and any carcinoma *in-situ*
30. Known or suspected abuse of illicit drugs or alcohol within 1 year prior to the Screening Visit
31. In the opinion of the Principal Investigator (PI), any other condition that will preclude participation in the study

Test Products, Dosage, and Mode of Administration:

Lorundrostat will be provided in 12.5 mg, and 25 mg tablets (equivalent to 14.74 mg, and 29.48 mg of lorundrostat monohydrobormide [HBr]). The daily dose of lorundrostat will not exceed 25 mg.

Lorundrostat: 25 mg tablets taken orally QD at approximately the same time each morning for 4 weeks.

Reference Product, Dosage and Mode of Administration:

Lorundrostat-placebo: Tablet matching the appearance of lorundrostat but without active substance, administered analogously to lorundrostat.

Duration of Subject's Participation Including Follow-up:

The expected duration of the study for each subject from Screening to the End of Study visit is expected to be:
Approximately 18 weeks

Statistical Methods:

Analysis Sets

The intent-to-treat (ITT) analysis set includes all subjects, regardless of whether treatment was received.

The full analysis set (FAS) will include all subjects who receive at least one dose of study drug. Subjects will be categorized according to the treatment assignment.

The safety analysis set (SAF) will include all subjects who receive at least one dose of study drug. Subjects will be categorized according to the treatment received in the respective study periods.

The population pharmacokinetics (popPK) analysis set will include all subjects who received at least one dose of lorundrostat and had at least one evaluable popPK sample taken. Subjects in this analysis set will be categorized according to the treatment received.

Sample Size

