2.3.1.6. Risk of Ketoacidosis

Ketoacidosis has been reported infrequently (estimated to be no greater than [REDACTED] in diabetic subjects taking SGLT2i, including rare fatal cases. Subjects with a history of at least 1 severe hypoglycemic event or severe diabetic ketoacidosis event in the 12 months prior to Screening will be excluded from

the trial. Subjects will be monitored for signs and symptoms of ketoacidosis, as well as predisposing conditions such as volume depletion.

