2.3.1.7. Risk of Acute Kidney Injury and Impairment in Renal Function

There have been post marketing reports of acute kidney injury, some requiring hospitalization and dialysis in patients receiving SGLT2i. Otherwise, small clinically insignificant and reversible decreases in eGFR are commonly observed following the initiation of SGLT2i and are likely related to mild volume depletion. Many of these episodes may have been related to volume depletion, congestive heart failure (CHF) and ketoacidosis. Subjects with severe CHF, ketoacidosis and need for renal replacement therapy will be excluded. Subjects will be monitored for signs and symptoms of acute kidney injury.

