2.3.1.8. Risk of Hypoglycemia

Hypoglycemia is a rare finding in non-diabetic subjects. A recent systematic review of SGLT2i (Teo 2021) found the incidence of hypoglycemia in non-diabetics was [REDACTED]. Adding SGLT2i to the T2DM treatment regimen is expected to lower blood glucose level and may cause hypoglycemia. All subjects will be monitored for signs and symptoms of hypoglycemia. Subjects with T2DM may be instructed to monitor their blood glucose level more closely upon initiation of study drug. Baseline treatment for T2DM will be adjusted, as needed, to avoid hypoglycemia.

2.3.1.9. Risk of Urosepsis and Pyelonephritis, Lower Limb Amputation, Genital Mycotic Infections, Necrotizing Fasciitis of the Perineum (Fournier's Gangrene)

All these conditions were observed rarely in clinical trials of SGLT2i. Subjects with a history of these conditions will be excluded from this study. All subjects will be monitored for the signs and symptoms of these conditions.

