2.3.1.12. Overall Benefit-Risk Conclusion

Considering the measures taken to minimize risk to subjects participating in this study, the potential risks are justified by the anticipated benefits that may be afforded to subjects with hypertension and CKD.

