8.1 Demographics and Other Baseline Characteristics

8.1.1. Medical History

Medical history data are to be collected at the Screening Visit. For female subjects of childbearing potential, the date of the last menstrual period should be noted. Data will be updated at subsequent visits, as appropriate.

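### Protocol Section 5.2 omits synopsis exclusion 27 (severe hypoglycaemia, severe ketoacidosis or impaired hypoglycaemia awareness), and Section 2.3.1.6 gives a different event threshold

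*Protocol*

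**What the plan says.** Synopsis exclusion 27 reads "Diabetes mellitus with >1 severe hypoglycemic event or severe diabetic ketoacidosis event (events requiring external help) in the 12 months prior to Screening", and goes on to exclude a history of impaired hypoglycaemia awareness.

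Section 5.2 passes from item 26 (HbA1c above 10%) to "27. Planned major surgery requiring hospitalization during the study period or performed within 4 weeks prior to the Screening Visit", which is synopsis item 28. None of its 30 items mentions hypoglycaemia, ketoacidosis or hypoglycaemia awareness.

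Section 2.3.1.6, on the ketoacidosis risk of SGLT2 inhibitors, puts the rule this way: "history of at least 1 severe hypoglycemic event or severe diabetic ketoacidosis event in the 12 months prior to Screening will be excluded".

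Section 2.3.1.7, on acute kidney injury, says: "Subjects with severe CHF, ketoacidosis and need for renal replacement therapy will be excluded".

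Two places deal with managing hypoglycaemia rather than excluding for it. Section 2.3.1.8 says "Baseline treatment for T2DM will be adjusted, as needed, to avoid hypoglycemia". Section 5.3 has the PI review diet, diabetes regimen and glucose monitoring before Randomization in subjects with T2DM. It also asks for extra glucose monitoring in subjects on insulin and/or metformin whose history shows that they are prone to hypoglycaemia.

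**The concern.** Section 5.2 is the body-text eligibility list, and Section 8 allows no waivers from the protocol. An exclusion that stands in the synopsis and is promised in the risk section, but not in Section 5.2, leaves sites with conflicting instructions on a safety rule.

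The rule has a stated purpose. Section 2.3.1.6 gives it as mitigation for ketoacidosis on SGLT2 inhibitors and notes that rare fatal cases have been reported. Sections 4.5 and 6 allow study dapagliflozin to be started in SGLT2i-naive subjects. Section 2.3.1.12 then concludes: "Considering the measures taken to minimize risk to subjects participating in this study, the potential risks are justified by the anticipated benefits". If Section 5.2 was the list applied, one of those measures was not operating as a defined criterion.

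The parallel case in Section 2.3.1.9 was carried through. For urosepsis, amputation, genital mycotic infection and Fournier's gangrene it says "Subjects with a history of these conditions will be excluded from this study", and that exclusion does appear in Section 5.2, as item 24.

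**Working it through.** No sample-size, power or alpha figure is involved, so the check is a comparison of texts.

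**Step 1: match the two lists.** Items 1 to 26 agree in topic. After that:

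| Number | Synopsis | Section 5.2 |
|---|---|---|
| 27 | Severe hypoglycaemia, ketoacidosis, impaired awareness | Planned or recent surgery |
| 28 | Planned or recent surgery | Malignancy |
| 29 | Malignancy | Drug or alcohol abuse |
| 30 | Drug or alcohol abuse | PI opinion |
| 31 | PI opinion | (none) |

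Synopsis items 28 to 31 are Section 5.2 items 27 to 30. The count is 31 − 30 = 1 unmatched criterion, and it is synopsis 27. The numbering in Section 5.2 is continuous with no redaction mark at this point, so neither a blacked-out item nor a PDF-reading gap explains it.

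**Step 2: compare the thresholds.** The synopsis needs more than one event in 12 months; its grammar leaves unclear whether that count also governs ketoacidosis. Section 2.3.1.6 needs at least one event in 12 months and is silent on awareness. Section 5.2 has no threshold.

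**Step 3: apply each text to a diabetic subject.** Events are within 12 months before Screening, and the last column counts specific criteria only.

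| Subject | Synopsis 27 | Section 2.3.1.6 | Section 5.2 |
|---|---|---|---|
| Exactly one severe hypoglycaemic event | Not excluded | Excluded | Not excluded |
| Two or more severe hypoglycaemic events | Excluded | Excluded | Not excluded |
| Exactly one severe ketoacidosis event | Depends on reading | Excluded | Not excluded |
| Two or more severe ketoacidosis events | Excluded | Excluded | Not excluded |
| Impaired awareness, no severe event | Excluded | Not addressed | Not excluded |

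The first row separates the two faults. With one severe hypoglycaemic event the synopsis would not exclude either, so restoring its wording in Section 5.2 would change nothing for that subject; the conflict there is purely more than one against at least one. The omission itself bites on repeat events and impaired awareness, and on a single ketoacidosis event if the count does not govern it. Even where the count does, Section 2.3.1.6 still promises exclusion and Section 5.2 does not deliver it.

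**The case against.** The best defence is that the criterion is in the protocol: the synopsis carries a full list in binding terms, and nothing shows which list the sites, eCRF or randomization system used. That is right. It limits the claim to what a site applying Section 5.2 would do, and a reader should not infer that such subjects were in fact enrolled.

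Second, Section 5.3 expects some hypoglycaemia-prone subjects to take part and manages them by monitoring, which fits deliberate removal as well as oversight. This is a real partial safeguard, as are PI discretion (Section 5.2 item 30) and ketoacidosis monitoring. None is a mandatory exclusion, and the extra glucose monitoring is for hypoglycaemia in subjects on insulin and/or metformin, not for prior ketoacidosis. SAP Section 1.2 says that Amendment 3 was partly meant to ease enrolment, but does not mention this criterion. The detailed change list is a separate document (protocol Section 12.7), so intent cannot be settled either way. Deliberate removal would still leave the synopsis and Section 2.3.1.6 wrong.

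Third, Section 2.3.1.7 might be taken as a further version of the rule. The text does not support that. It is loose narrative about kidney injury, gives no severity, count or window for ketoacidosis, does not mention hypoglycaemia, and can be read as current ketoacidosis. It needs clarifying, no more.

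Fourth, a reader might infer that the shifted numbers make the screen-failure listing ambiguous. That holds only if the listing is coded by criterion number, which SAP Section 6.3.1 does not say.

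**Conclusion.** The point stands as one omission and one threshold conflict in a safety eligibility rule. It goes beyond a clerical slip, because following Section 5.2 literally admits subjects whom the synopsis and the stated ketoacidosis mitigation exclude. It should be corrected.

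Its size can be given only in text terms: one criterion missing from Section 5.2, and two different event thresholds where the rule is stated. How many subjects it touches cannot be derived from the documents. The practical consequence assumes that at least some sites worked from Section 5.2, which the documents neither confirm nor exclude.

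A reader might go further and infer that the trial's efficacy result is compromised. Nothing supports that: the primary endpoint, alpha, power and analysis-set definitions do not depend on this criterion.

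**What to change.** 1. Confirm from the Amendment 3 summary of changes which text was intended.
2. Unless the removal was deliberate, restore the criterion in Section 5.2, including impaired awareness, and use one threshold in the synopsis, Section 2.3.1.6 and Section 5.2. At least one event matches the stated mitigation, at the cost of excluding some more diabetic subjects. State explicitly that the count applies to hypoglycaemia and ketoacidosis alike.
3. If the removal was deliberate, correct the synopsis and Section 2.3.1.6 instead.
4. Clarify in Section 2.3.1.7 whether current or past ketoacidosis is meant.
5. SAP Section 1.2 says that the study was completed under this amendment, so rewording alone protects no enrolled subject. State before database lock, when SAP Section 4.2 has deviations finally classified, which wording governed eligibility and deviation classification.
6. Report in the CSR any randomized diabetic subject whose recorded medical history meets the criterion. A subject who meets only a wording not in force should be described as safety information, not as a deviation.

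The cost is a wording correction in a few places, a review of the medical history listing (SAP Section 6.3.3) for the diabetic subjects among the approximately 60 planned, and a short CSR statement. One limit should be declared with it. Protocol Section 8.1.1 says "Medical history data are to be collected at the Screening Visit" but does not say that event count, need for external help or a 12-month window is recorded, so the review may not classify every subject. Retrospective source queries to fill that gap would go further than the point requires.
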